- 3) *Epistaxis Severity Score (ESS) ≥ 4 and 2 or more nosebleeds per week with a cumulative nosebleed duration of at least 5 minutes per week*
- 4) Stable nasal hygiene and medical regimen for preceding 1 month
- 5) Stable epistaxis pattern over the preceding 3 months

Exclusion Criteria:

- 1) Contraindications for systemic β adrenergic blocker administration
 - a. Hypersensitivity to β adrenergic blockers
 - b. Asthma or bronchospasm
 - c. Congestive heart failure with LVEF <40%
 - d. Hereditary pulmonary arterial hypertension
 - e. Baseline bradycardia (HR <55 beats per minute)
 - f. Sick Sinus Syndrome
 - g. 2nd or 3rd degree heart block, left or right bundle branch block, or bifascicular block
 - h. Uncontrolled diabetes mellitus (most recent HbA1c >9%) or diabetic ketoacidosis within last 6 months
 - i. Hypotension (systolic blood pressure < 90)
- 2) Known hypersensitivity to timolol
- 3) Severe peripheral circulatory disturbances (Raynaud phenomenon)
- 4) Known intermediate or poor metabolizer variant of the liver enzyme CYP2D6
- 5) Current use of any of the following known strong CYP2D6 inhibitors: fluoxetine (Prozac), paroxetine (Paxil), bupropion (Wellbutrin), quinidine, quinine, ritonavir (Norvir), and terbinafine (Lamisil)
- 6) Current use of the following other drugs known to pharmacodynamically interact with timolol: diltiazem, verapamil, digoxin, digitalis, propafenone, disopyramide, clonidine, flecainide, or lidocaine
- 7) Patients currently treated or who plan to initiate treatment with β -blockers
- 8) Use of any anti-angiogenic medication in the last month prior to recruitment, including bevacizumab, pazopanib, thalidomide, or lenalidomide
- 9) Illicit drug use, except marijuana
- 10) Known pheochromocytoma
- 11) Use of anticoagulants, antiplatelet, or fibrinolytic therapies within the last month prior to recruitment, except for low-dose (81 mg or less) of aspirin
- 12) Pregnancy or planned pregnancy in the next 6 months or currently breastfeeding
- 13) Inability to read or understand English

- 14) Inability to complete 8 weeks of therapy for any reason

Eligibility Determination

To determine potential eligibility for the study, the research team will query the medical record based on the following inclusion/exclusion criteria:

- Age (18 years or older)
- Medication history to assess current use of a β -blocker (exclusion)
- Allergy history to timolol (exclusion)
- Changes in epistaxis care in the last month (exclusion)

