If patients are not able to use the app for any reason, a text message and/or email will be sent to the patient each evening via the REDCap™ (Research Electronic Database) website that will ask questions about the frequency and severity of epistaxis and energy level that replicates the Cure HHT app. The REDCap™

survey will assess for compliance by asking if the research subject has used the assigned treatment that day. Once each week, the survey will ask the subject if he or she received a blood transfusion that week. REDCap™ is a password-protected site that will keep the information confidential.

Methods

Demographic information, including age, gender, and race, will be collected from each enrolled patient. Data will be collected regarding the duration of each patient's epistaxis history, previous treatments, and estimation of the average number of nosebleeds per day; HHT treatment history; co-morbid conditions, such as hypertension, inhalant allergies, and other blood dyscrasias; risk factors, such as cigarette smoking, use of CPAP, and use of supplemental oxygen; and medications associated with increased bleeding.

At the initial visit, research subjects will complete the informed consent process, *SF-36*, *ESS*, baseline electrocardiogram (ECG), CYP2D6 enzyme allele, blood pressure (BP), and heart rate (HR). ECGs are to be read by [name]. Subjects will undergo a directed otolaryngology physical exam by [name] that will include nasal endoscopy to describe nasal mucosa telangiectasias. [name] will rate the nasal mucosa telangiectasias using the *HES*. Patients will be scheduled for phlebotomy to obtain a blood specimen to measure hemoglobin levels prior to beginning therapy. Baseline daily iron supplementation will also be recorded and it will be recommended to the patient not to alter their daily supplementation of iron or other treatments, unless indicated by a change in epistaxis frequency.

Upon demonstration that patient does not have the CYP2D6 allele associated with a low or intermediate metabolizer of timolol and successful completion of questionnaires, physical examination, and laboratory tests, subjects will be randomized to receive either timolol gel or placebo.

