Pharmaceutical Preparation. The intervention will be prepared and dispensed by Advanced Rx Pharmacy, Plymouth Meeting, Pennsylvania. Timolol nasal gel 0.1% will be prepared with a poloxamer gel (combination of poloxamer 188 and 407; pH adjusted to 4.5-6.5) and 0.5 ml applied to each nostril twice daily. The total daily dose would amount to 2 mg. Placebo gel is prepared with poloxamers and no active ingredients. Timolol is odorless so the research subjects should not be able to identify the placebo gel from the active gel.

Subjects will be instructed to apply 0.5 ml to the nasal mucosa of each nostril twice daily via 20 mL syringes. The gel will be dispensed in an amber vial with an adapter to which the syringe can attach in order to draw out the medication for each dose. Patients will be supplied with one syringe per day for a total of 56 syringes. They will be given alcohol wipes to clean the syringe between the morning and evening gel application. When the syringes are distributed, the research assistants will make sure that the patient understands how to apply correctly the medication to the nasal cavity.

BP and HR measurements will be obtained by the subject weekly at home with the use of the blood pressure monitor given to them at the beginning of the study and blood pressures will be reported via the use of REDCap™. Subjects will also be instructed to report any local or systemic side effects throughout the duration of the study. Telephone calls with the study team at the end of Week 1 and again at Week 4 will be arranged.

After 8 weeks of intervention, subjects will be asked to return to clinic and the physician will perform nasal endoscopy and complete the *HES* scale. Subjects will have blood pressure and heart rate measurements. Subjects will complete the *SF-36*, *ESS*, *CGI*, *EQQoL*, and the *TSQMII* questionnaires. To assess the quality of the blind, subjects will be asked which arm of the study they thought they were randomized. Subjects

will also be asked whether they would recommend the treatment to a friend or family member if they suffered with HHT-associated epistaxis. A follow-up blood draw to measure hemoglobin and hematocrit will be completed.

It will be emphasized to the patient not to change their current nasal hygiene regimen (e.g., nasal saline spray) or other chronic treatments (e.g., tranexamic acid).

[figure not shown]
Primary Outcome:

- 1) Mean change in Epistaxis Severity Score (ESS) between baseline and follow-up.

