delivery.(Jagdale, Shewale, and Kuchekar 2016) The authors studied timolol and Poloxamer 407 polymer interaction and were able to show that there was no chemical reaction between timolol and the polymer.(Nieminen et al. 2007; Volotinen et al. 2011) The authors also demonstrated no histological changes to nasal mucosa after the study. The authors concluded that the combination of timolol with Poloxamer 407 was associated with adequate gelation temperature, mucoadhesive strength, and *in situ* controlled release of timolol. They concluded that timolol gel is safe for nasal administration. Second, Olitsky studied intranasal delivery of one drop of timolol 0.5% as ophthalmic solution to each nostril three times daily for a total daily dose of 1.5 mg in one adult patient with HHT-associated epistaxis.(Olitsky 2012) The drug was well tolerated with no change in blood pressure or heart rate; no other side effects were reported. Third, timolol 0.5% ophthalmic drops administered intranasally has been associated with systemic side effects, especially in patients with CYP2D6 enzyme variants.(Epperla, Brilliant, and Vidaillet 2014) Ocular administration of timolol has been associated with systemic adverse effects, including bradycardia.(Canpolat et al. 2013; Nieminen et al. 2007; Volotinen et al. 2011) (See Appendix 6 – Adverse Reactions). Among the various symptoms of systematically absorbed ophthalmic timolol, change in heart rate is the most frequent and is more likely with the 0.5% aqueous rather than the 0.1% hydrogel formulation.(Nieminen et al. 2007) Since the pharmacokinetics of timolol are dependent on the CYP2D6 polymorphic enzyme, the individual patient phenotype for this enzyme will dictate plasma concentrations and frequency of adverse events. Four major phenotypes of CYP2D6 metabolizers have been identified: *Poor*, *Intermediate*, *Extensive*, and *Ultrarapid*.(Ingelman-Sundberg and Rodriguez-Antona 2005; Sikka et al. 2005; Volotinen et al. 2011) In one study, it was found that *Poor* metabolizers had a 2.5-fold higher plasma concentration than *Extensive* metabolizers after application of timolol 0.5% aqueous eye drops.(Nieminen et al. 2007). Timolol eye drops delivered intranasally was associated with greater β -blockade in *Poor* metabolizers as compared with *Extensive* metabolizers. Thus, the metabolism of systematically absorbed timolol is clearly related to the phenotype of the individual for the CYP2D6 enzyme.

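### Weekly home and week-8 BP/HR readings are not timed to gel application and time since application is not recorded, so asymptomatic stop-limit breaches may be found late or, at a habitual trough, missed

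*Combined protocol and SAP*

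**What the plan says.** Home monitoring is described in Section VII (Methods): "BP and HR measurements will be obtained by the subject weekly at home with the use of the blood pressure monitor given to them". Section X repeats the weekly schedule and adds that subjects are trained on the device at baseline. For the week-8 visit the plan says only "Subjects will have blood pressure and heart rate measurements".

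Gel is applied twice a day, morning and evening ("They will be given alcohol wipes to clean the syringe between the morning and evening gel application"). Dosing data are limited to use or non-use. The app asks whether medication was taken; for subjects who cannot use the app, the REDCap "survey will assess for compliance by asking if the research subject has used the assigned treatment that day".

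The stop list in Section X includes an asymptomatic systolic pressure below 80 mmHg or 20% below baseline, and a heart rate below 50/min with no symptom required. On systemic effects of ophthalmic timolol, Section X says "change in heart rate is the most frequent and is more likely with the 0.5% aqueous rather than the 0.1% hydrogel formulation". Entry excludes "Baseline bradycardia (HR <55 beats per minute"), so a subject may start at 55.

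**The concern.** The two limits that need no symptoms depend wholly on BP/HR readings. Side-effect reports, the Week 1 and Week 4 calls and the 24-hour phone line pick up what the subject feels. The plan describes no on-treatment ECG and no observed post-dose reading. Between visits, a silent fall is found only if a self-timed weekly reading coincides with it.

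If the effect rises and wanes within the 12-hour dosing interval, the chance of finding it depends on when the subject measures, which the plan leaves open. Because time since application is not captured, a normal value at trough cannot later be told from a normal value at peak. That weakens individual safety monitoring, the safety profile in Aim 3, and what the trial can pass on to a Phase III design.

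**Working it through.** The plan states no figure on this point, so there is none to reproduce. The text comparison comes first, then an illustration.

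**Text.** Home readings: weekly, no clock time or interval from dose (Sections VII and X). Week-8 reading: no interval from dose. Compliance items: used or not, no time. Applications: 56 days x 2 = 112, against eight home readings and one clinic reading. Heart-rate margin: a subject entering at 55 crosses the limit with a 6-beat fall (55 - 6 = 49).

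**Simple illustration.** Suppose a breach lasts w hours after each 12-hourly dose. Eight independent random-time readings include at least one breach with probability 1 - (1 - w/12)^8: 50% for w = 1, 77% for 2, 90% for 3, 96% for 4. A subject who always reads just before a dose has probability 0 for any w below 12.

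**Model.** All kinetic inputs are assumptions. One compartment, steady state, 12-hourly dosing. Exposure at t hours is proportional to exp(-kt)/(1 - exp(-12k)) - exp(-ka t)/(1 - exp(-12 ka)), with k = ln2/half-life (limiting form if ka = k). Half-lives are 2, 3, 4, 5 and 6 h. Absorption rates ka are 1, 2, 3 per hour (15 fast cases, peak at 0.8-2.1 h) and ln2/2, ln2/3, ln2/4 per hour (15 slow cases, peak at 2.7-4.4 h). Effect is proportional to exposure, and r is exposure divided by its peak. A 25% systolic fall at peak meets the 20% limit when r is at least 20/25 = 0.80. The same threshold fits a heart rate of 60 falling to 47.5: (60 - 50)/(60 - 47.5) = 0.80.

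- **Always just before a dose:** r is 0.023-0.361 (fast) and 0.168-0.708 (slow), so the 25% fall is seen in 0 of 30 cases. Larger falls begin to show in slow cases: a 35% fall (20/35 = 0.57) in 5 of 15 and a 40% fall (20/40 = 0.50) in 8 of 15; fast, none at either.
- **Random times:** the share f of the interval with r at or above 0.80 is 0.12-0.36 (fast) and 0.325-0.80 (slow). By the third reading, 1 - (1 - f)^3 is 32-74% and 69-99%. By the eighth, 1 - (1 - f)^8 is 64-97% and 96-100%.
- **Spread evenly within 2 h either side of a dose, eight readings:** 95-99% (fast) and 81-98% (slow).
- **Spread evenly over 1-4 h after a dose:** the share g of that window at or above 0.80 is 0.26-1.00 (fast) and 0.92-1.00 (slow). By the third reading, 1 - (1 - g)^3 runs from 1 - 0.74^3, about 60%, to 100% (fast) and exceeds 99% (slow).

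**Sensitivity to effect shape.** With a saturating effect, r(1 + 0.1)/(r + 0.1), the 0.80 threshold is met once r reaches 0.08/0.30 = 0.27. A pre-dose reading then sees the 25% fall in 4 of 15 fast and 14 of 15 slow cases.

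Reading error is ignored throughout. The counts are over a chosen grid of inputs and are not detection rates in patients.

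**The case against.** The strongest reply is that the worst case needs a behaviour the documents do not show. A reader might infer that subjects will tend to measure just before the evening dose, because BP is reported through REDCap and "a text message and/or email will be sent to the patient each evening via the REDCap" system. The text does not support that. The message goes only to subjects who cannot use the app, it asks about use that day, and nothing says the reading is taken when it arrives. Nor is an evening habit a pre-dose habit: readings scattered within 2 h of a dose perform well in the model. Only a strict trough habit, or another fixed unfavourable time, produces a systematic miss. This part of the reply stands.

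It also stands that the size rests on assumption. The documents give no half-life, absorption rate or effect curve for this gel. For a related timolol-poloxamer gel, Section X reports "controlled release of timolol. They concluded that timolol gel is safe for nasal administration"; a flatter profile would make trough readings more informative, as the saturating case shows.

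The residual risk is narrow as well. Entry screens remove poor and intermediate CYP2D6 metabolisers, interacting drugs, low heart rate, low pressure and conduction block, and symptomatic falls have their own routes. Baseline training might cover timing, and the design figure is not shown, but no text says that it does.

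What survives is that timing is uncontrolled and unrecorded. Even without a trough habit, detection in fast cases can be late (32-74% by the third reading).

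**Conclusion.** The point holds as a cheap improvement, with medium confidence. The plan sets limits that only a reading can trigger and leaves the timing of that reading to the subject, unrecorded. An asymptomatic fall that peaks after a dose may be found weeks late, or missed by someone who always reads at trough. How often this would happen cannot be stated from the documents.

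Three stronger readings are not supported. The modelled counts do not show that breaches will generally be missed: varied self-chosen times catch most larger falls over eight weeks. They do not justify an exact schedule such as 1.5 h and 3 h either: the case for one turns on 22% versus 20% falls, which at an assumed baseline of 120 mmHg differ by 0.02 x 120 = 2.4 mmHg on a single home reading. And the BP/HR comparison between arms is not biased, because the blinded placebo arm measures under the same rules. The primary and secondary outcomes are not affected.

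**What to change.** In Section VII (Methods) and Section X, instruct subjects in both arms to take the existing weekly reading in the first few hours after an application and not just before one: about 1-4 h, varied across weeks, or at the product's time to peak if the sponsor knows it. Add two REDCap fields, time of last application and time of reading, and record both at week 8. Apply the stop criteria to every reading, whenever taken. Summarise BP/HR by arm on all readings, with time since application as an extra summary.

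The cost is one line of instructions, two REDCap fields and a timing entry on the week-8 form, with no added reading, device or visit. The downside is slight inconvenience and some off-schedule readings, which are still used. Eight home readings will still sample few of the 112 applications.

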The mechanisms of action, published literature, and results of an unpublished study presented at the 13th HHT International Scientific Conference suggest a role of β -blockers in the management of HHT-associated epistaxis. The work by Mei-Zahav et al suggest propranolol gel may be an effective treatment for HHT-associated epistaxis. However, intranasal propranolol is not well tolerated and is associated with arrested cilia movement. Topical timolol has advantages over propranolol in that it is well-tolerated and has been shown to not have an effect on nasal mucosa.(Jagdale, Shewale, and Kuchekar 2016) Patients with certain pre-existing heart conditions or metabolizing variants of the liver enzyme CYP2D6 are at increased risk for adverse effects of timolol ophthalmological solution.

Given our understanding of the pathophysiology of HHT-associated epistaxis, mechanism of action, and pharmacokinetics of intranasal timolol, we believe it is now appropriate to conduct a Phase II double-blinded, placebo controlled randomized clinical trial to evaluate the efficacy of intranasal timolol gel. The results of this Phase II study will provide additional information on the benefits and risks of intranasal timolol, which can be used to inform the design of a definitive Phase III study.

VI. SPECIFIC AIMS

The Specific Aims are to determine in adults with HHT-associated epistaxis:

1. If topical timolol gel is more effective than placebo in reducing the frequency and severity of epistaxis.
2. If topical timolol gel is more effective than placebo in improving hemoglobin levels.
3. The frequency of adverse events, side effects, and safety profile of topical timolol gel delivered to the nasal mucosa, and safety profile of topical timolol gel delivered to the nasal mucosa of HHT patients.

VII. DESIGN PLAN

Study Type

The study will be a multi-site, double-blind, placebo-controlled randomized clinical trial performed at two tertiary academic medical center HHT Centers of Excellence.

Blinding

Research participants and the members of the investigative team who will have direct subject interaction will be blinded to treatment assignment. The research statistician, [name], will not be blinded. All subject assessments will be performed without knowledge of treatment.

Study Population

Inclusion Criteria:

- 1) Adults ages 18 and older
- 2) Confirmed clinical (meeting at least 3 of the 4 Curaçao Criteria) or genetic diagnosis of HHT

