Secondary Outcomes:

- 1) Clinical Global Impression – Improvement (CGI-I) Score
- 2) Mean change in hemoglobin
- 3) Change in intensity of telangiectasias in the nasal mucosa as determined by the HHT endoscopic scale (HES)

Summary of Project Design

VIII. SAMPLE SIZE AND PLANNED STATISTICAL ANALYSIS

Sample Size

Sample size estimate for the proposed study were derived from the single study(Ichimura et al. 2016) of within subject change in severity of epistaxis associated with timolol ophthalmic solution (0.5%) as a nasal drop. In that study, 9 of the 11 subjects (82%) experienced a reduction in the severity of bleeds as measured on a 5-point Likert scale. We hypothesize a similar response (82%) in our proposed study among subjects randomized to receive timolol gel and a 20% response rate among subjects randomized to placebo gel, corresponding to a difference of 62%.

A power analysis was performed using Fisher’s exact test in G-Power 3.1.2. We estimate that a total sample size of 24 patients (ie., 12 in each arm) is needed to allow us to detect with 80% power at the 2-sided alpha level of 0.05 a difference of 62% or more in the percent of subjects who experience reduction of severity of

bleeds between treatment groups. Considering a 20% drop out rate, we plan to enroll 30 subjects in the study.

Statistical Analysis

Standard descriptive statistics will be used to describe distribution of baseline characteristics in each of the study groups. The effect of the intervention will be measured as the difference in the within-subject change (baseline – 8-week follow-up) in *ESS* scores between the two treatment groups calculated as shown below.

1) Within subject difference with each treatment group

$$\begin{aligned}\Delta ESS_{\text{Timolol}} &= (ESS_{\text{Timolol_base}} - ESS_{\text{Timolol_8-Week}}) \\ \Delta ESS_{\text{Control}} &= (ESS_{\text{Timolol_base}} - ESS_{\text{Timolol_8-Week}})\end{aligned}$$

2) Between treatment difference

$$\Delta ESS_{\text{Timolol}} - \Delta ESS_{\text{Control}}$$

The 95%CI around this effect size will be determined to assess the precision of the observed effect and whether a clinically meaningful difference is plausible given the observed results.

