Frequency of Different CYP2D6 Alleles in the Population

The frequency of different CYP2D6 alleles and thus the ability to metabolize timolol was studied in population of 104,509 de-identified patient samples from across the United States between February 2015 and March 2016.(Del Tredici et al. 2018) The frequency distribution of various phenotypes of CYP2D6 alleles was observed to be: ultra-rapid metabolizers (2.2%), normal metabolizers (81%), intermediate metabolizers (11%), and poor metabolizers (6%). Therefore, an estimated total of 17% or 5 subjects otherwise eligible for the study would be expected to be at increased risk of side effects due to timolol compared to the normal metabolizers and therefore will be excluded.

While ophthalmic solution is readily absorbed into the blood stream, CYP2D6 genetic testing is not commonly done for open-angle glaucoma patients prior to initiation of timolol therapy. To prevent cardiovascular side effects, it is recommended that glaucoma patients be screened for coexisting conditions and consideration of genetic phenotypic CYP2D6 status testing if readily available.(Maenpaa and Pelkonen 2016)

In this study, all eligible patients will undergo CYP2D6 testing, ECG, BP, and HR readings at initial visit. Patients with a CYP2D6 allele that is associated with an intermediate or poor metabolizer or an ECG that demonstrates conduction abnormalities, such as second-degree and third-degree AV block and/or clinically significant bradycardia will be excluded from the study. Enrolled patients will be given a blood pressure monitor by the study team and taught how to use it at their baseline visit. They will be instructed to take and report weekly BP and HR to the study team in addition to local or systemic side effects. Patients

will be called at the end of Week 1 and Week 4 of the study to answer any questions or concerns they may have as well as to ask if they have experienced any side effects. During these phone calls, patients will be asked whether they have changed their daily iron supplementation or blood transfusion pattern from baseline. If patients have an increase in nosebleeds for any reason, they will be asked to contact the study team or report to the emergency department, depending on the severity.

Any of the following will be considered an indication to stop the study:

- 1) Asymptomatic systolic BP drop to less than 80 mmHg or a drop of 20% from baseline systolic BP
- 2) Symptomatic blood pressure drop

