Appendix 5.
Treatment Satisfaction Questionnaire for Medication Version II
(TSQMII)

Patient ID _____ **Date** _____

- 1) How satisfied or dissatisfied are you with the ability of the medication to prevent or treat your condition?
 - 1 Extremely Dissatisfied
 - 2 Very Dissatisfied
 - 3 Dissatisfied
 - 4 Somewhat Satisfied
 - 5 Satisfied
 - 6 Very Satisfied
 - 7 Extremely Satisfied

- 2) How satisfied or dissatisfied are you with the way the medication relieves your symptoms?
 - 1 Extremely Dissatisfied
 - 2 Very Dissatisfied
 - 3 Dissatisfied
 - 4 Somewhat Satisfied
 - 5 Satisfied
 - 6 Very Satisfied
 - 7 Extremely Satisfied

- 3) As a result of taking this medication, do you experience any side effects at all?
 - 1 Yes
 - 0 No

- 4) How dissatisfied are you by side effects that interfere with your physical health and ability to function (e.g., strength, energy levels)?
 - 1 Extremely Dissatisfied
 - 2 Very Dissatisfied
 - 3 Somewhat Dissatisfied
 - 4 Slightly Dissatisfied
 - 5 Not at all Dissatisfied

- 5) How dissatisfied are you by side effects that interfere with your mental function (e.g., ability to think clearly, stay awake)?
 - 1 Extremely Dissatisfied
 - 2 Very Dissatisfied
 - 3 Somewhat Dissatisfied
 - 4 Slightly Dissatisfied
 - 5 Not at all Dissatisfied

- 6) How dissatisfied are you by side effects that interfere with your mood or emotions (e.g., anxiety/fear, sadness, irritation/anger)?
 - 1 Extremely Dissatisfied
 - 2 Very Dissatisfied
 - 3 Somewhat Dissatisfied

- 4 Slightly Dissatisfied
- 5 Not at all Dissatisfied

- 7) How satisfied or dissatisfied are you with how easy the medication is to use?
- 1 Extremely Dissatisfied
 - 2 Very Dissatisfied
 - 3 Dissatisfied
 - 4 Somewhat Satisfied
 - 5 Satisfied
 - 6 Very Satisfied
 - 7 Extremely Satisfied
- 8) How satisfied or dissatisfied are you with how easy it is to plan when you will use the medication each time?
- 1 Extremely Dissatisfied
 - 2 Very Dissatisfied
 - 3 Dissatisfied
 - 4 Somewhat Satisfied
 - 5 Satisfied
 - 6 Very Satisfied
 - 7 Extremely Satisfied
- 9) How satisfied or dissatisfied are you by how often you are expected to use/take the medication?
- 1 Extremely Dissatisfied
 - 2 Very Dissatisfied
 - 3 Dissatisfied
 - 4 Somewhat Satisfied
 - 5 Satisfied
 - 6 Very Satisfied
 - 7 Extremely Satisfied
- 10) How satisfied are you that the good things about this medication outweigh the bad things?
- 1 Extremely Dissatisfied
 - 2 Very Dissatisfied
 - 3 Dissatisfied

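### Aim 3 asks for adverse-event frequency, but no outcome, analysis or structured event record supports it, and several relevant symptoms have no stated baseline

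*Combined protocol and SAP*

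**What the plan says.** Aim 3, in the Abstract and in section VI, is to determine "The frequency of adverse events, side effects, and safety profile of topical timolol gel delivered to the nasal mucosa". The outcomes in section VII are change in ESS (primary) and CGI-I, hemoglobin and HES (secondary). Section VIII analyzes ESS and promises suitable analyses for the secondary outcomes; it describes none for adverse events.

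Side effects reach the study team by these routes:

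- **Open instruction** (section VII, Pharmaceutical Preparation): "Subjects will also be instructed to report any local or systemic side effects throughout the duration of the study".
- **Weekly report** (section X): "They will be instructed to take and report weekly BP and HR to the study team in addition to local or systemic side effects". No symptom item or form is named.
- **Calls at the end of Week 1 and at Week 4** (section X): subjects are called to answer questions or concerns, "as well as to ask if they have experienced any side effects".
- **Week 8 visit** (section VII): "Subjects will complete the *SF-36*, *ESS*, *CGI*, *EQQoL*, and the *TSQMII* questionnaires". TSQMII item 3 (Appendix 5) reads "As a result of taking this medication, do you experience any side effects at all", answered yes or no. Items 4 to 6 rate dissatisfaction with side effects on physical, mental and emotional function.

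The daily app or REDCap log covers epistaxis, energy, transfusion and compliance. The initial visit includes SF-36, ESS, ECG, blood pressure, heart rate, endoscopy with HES, and hemoglobin.

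**The concern.** An aim stated as a frequency needs a defined event, a denominator, a way of finding the events and a summary. The plan gives Aim 3 little beyond open reporting. A stopping criterion in section X refers to a side-effect grade, but no grading scale is named.

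This matters because section XII says that efficacy and safety in topical gel form are largely unknown, and section V says that the Phase II results on benefits and risks are to inform a Phase III design. If mild or late effects are reported only when a subject thinks to mention them, the frequency carried forward may be too low. If symptoms present before dosing are counted as events, the within-arm frequency is too high. The plan as written cannot show which error dominates.

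**Working it through.** **1. What each source can deliver for Aim 3**

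| Source | Asked directly? | Identifies the event and its timing? | Stated baseline? |
|---|---|---|---|
| Open instruction and weekly report | Instruction to report; no item named | Depends on the subject | No |
| Week 1 and Week 4 calls | Yes | No form described | No |
| TSQMII items 3-6, Week 8 | Yes, with attribution to the medication | No | Not listed |
| EQQoL, Week 8 | Yes (blocked nose, crusts, tired or breathless) | Frequency rating, no dates | Not listed |
| SF-36 vitality | Yes | Scale score only | Yes |
| HES crusting | Examined | Score only | Yes |
| BP, HR | Measured | Yes | Yes |

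An ECG is recorded at baseline. Fatigue, crusting and cardiovascular measures therefore have a starting value. Burning and rhinorrhea (section V, the propranolol gel trial) and congestion, headache and dizziness (Appendix 6) have none stated, although the documents themselves raise them as possible effects.

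**2. Number on timolol**

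Section VIII requires 24 subjects, 12 per arm, and allows 20% dropout: 24 / (1 - 0.20) = 30, which reproduces the planned enrollment. With equal allocation, 30 / 2 = 15 per arm. One missed case moves an arm's observed rate by 1/15 = 6.7 percentage points.

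**3. Chance of seeing an event at least once**

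For true rate p, capture fraction c and n = 15, the probability is 1 - (1 - pc)^15. The documents give neither p nor c, so both are assumed.

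| True rate | c = 100% | c = 75% | c = 50% |
|---|---|---|---|
| 10% | 1 - 0.90^15 = 79% | 1 - 0.925^15 = 69% | 1 - 0.95^15 = 54% |
| 5% | 1 - 0.95^15 = 54% | 1 - 0.9625^15 = 44% | 1 - 0.975^15 = 32% |

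**4. What small numbers do even with full capture**

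With 0 events in 15, the exact two-sided 95% upper limit is 1 - 0.025^(1/15) = 21.8%; with 0 in 12 it is 26.5%.

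**5. Between-arm comparison**

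If both arms capture the same fraction c, the observed risk difference is c times the true one. For assumed rates of 40% and 10% with 15 per arm, the exact power of Fisher's test at two-sided 0.05 is 32.5% with full capture and 8.3% with half captured in both arms.

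**The case against.** The plan collects more than a quick reading suggests. Subjects report side effects along with the weekly readings, so Weeks 5 to 8 are not without contact. The daily log asks about energy, the TSQMII separates three kinds of impact, and the EQQoL asks about a blocked nose and crusts. Section XII provides round-the-clock telephone access, and section XI has serious and unexpected adverse events investigated and reported. Randomization against a blinded vehicle gel balances pre-existing symptoms in expectation, which answers most of any worry about attribution. The propranolol experience does not demonstrate loss either: burning that resolves in one to two weeks is within reach of the Week 1 call, and rhinorrhea severe enough to cause withdrawal would hardly go unnoticed. A study-design figure in section VII is not shown in the text reviewed here and might list more visit content.

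All of this stands, and it rules out some stronger readings. A reader might infer that the event rate will be under-counted; the documents give no capture rate, so only a possible under-count can be claimed. A reader might infer that there is no baseline or no way to attribute effects; the baselines above and the vehicle arm contradict that. A reader might also take crusting in Appendix 6 as an expected nasal effect; there it is an ocular sign.

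None of it supplies an Aim 3 outcome, an event-level record or an analysis. The vehicle arm cannot separate vehicle effects from symptoms present before dosing within an arm, and it does not restore a risk difference shrunk by incomplete capture.

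**Conclusion.** The point holds in a limited form. Aim 3 has no outcome or analysis, its event data rest mainly on open reporting with two prompted calls, and several local and systemic symptoms have no stated baseline. Mild or late events may be missed, and within an arm new symptoms cannot be told from old ones.

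For an event with a true 10% rate and 15 subjects on timolol, going from full to 50% capture lowers the chance of seeing it at all from 79% to 54%. This rests on equal allocation, all 30 subjects enrolled, and an assumed capture range of 50% to 100%. Better collection would not remove the limit set by sample size: at full capture a 5% event is still seen only 54% of the time. This is a cheap improvement to the safety data; it does not affect the ESS comparison.

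**What to change.** - Use one short fixed symptom checklist with a named grading scale and no question of cause: nasal burning, rhinorrhea, congestion, crusting, headache, dizziness, fatigue, dyspnea, syncope, other.
- Give it at the initial visit before dosing, in the weekly REDCap blood pressure and heart rate report, in the Week 1 and Week 4 calls, and at Week 8.
- List as the Aim 3 outcome the proportion per arm with each treatment-emergent event, defined as new or worse than baseline, with exact 95% confidence intervals and a stated denominator.

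The cost is about ten tick-boxes at contacts already planned and one descriptive table. Sample size, eligibility and treatment are unchanged. The downside is slightly more burden on subjects and, because prompting raises reported counts in both arms, rates that should be read against the placebo arm.
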